5. STUDY OBJECTIVES AND ENDPOINTS

5.1 Primary Objective:

- Determine the magnitude of the early steps of fatty acid oxidation in glioma using ^{18}F -FPIA PET/MRI.

5.2 Secondary objective:

- Compare magnitude of tracer-derived biochemical uptake measure with tumour grade.

5.3 Tertiary objective:

- Compare magnitude of tracer-derived biochemical uptake measure with ex vivo gene expression specifically for metabolism.
- Compare magnitude of tracer-derived biochemical uptake measure with ex vivo tissue metabolite analysis using Mass Spectrometry (MS).
- Compare the magnitude of tracer-derived biochemical uptake measure with ex vivo protein and phosphoprotein analysis from the major cell proliferation and survival pathways including phospho ERK 1/2 and pSer641.
- Comparison of flux constants derived from mathematical modelling of ^{18}F -FPIA PET/MRI data with tumour grade, contrast enhancement and perfusion.

6. STUDY ENDPOINTS

6.1 Primary Endpoint:

- Quantitative measurement of ^{18}F -FPIA uptake in human gliomas.

6.2 Secondary endpoint:

- Correlation of ^{18}F -FPIA uptake with tumour type and histological grade including O⁶-methylguanine-DNA methyltransferase (MGMT) and isocitrate dehydrogenase (IDH) gene expression.

6.3 Tertiary endpoint:

Measuring fatty acid oxidation in gliomas using ^{18}F -FPIA Version 1.0_01/02/2018 IRAS: 228245

- Correlation of ¹⁸F-FPIA uptake with expression of genes responsible for metabolism on tissue obtained after surgery.
- Correlation of ¹⁸F-FPIA uptake with tissue metabolites obtained after surgery.
- Correlation of ¹⁸F-FPIA uptake with tissue proteins and phosphoproteins obtained after surgery.
- Correlation of ¹⁸F-FPIA flux constants with histological grade.
- Correlation of ¹⁸F-FPIA variables with structural and functional MRI variables including perfusion.

7. STUDY OUTLINE

[figure not shown]
7.1 Study Design

10 evaluable patients with suspected cerebral glioma on previous MRI who are due to undergo surgical resection or biopsy will be enrolled into the study. The patients invited to participate in the study will provide full consent, but will only undergo ¹⁸F-FPIA PET/MRI imaging once they have satisfied the inclusion and exclusion criteria in section 8. Once these have been satisfied, eligible patients will proceed to ¹⁸F-FPIA PET/MRI.

On the day of imaging the patients will undergo a blood test to measure plasma concentrations of carnitine. During the scan, a single dose of ¹⁸F-FPIA (maximum, 370 MBq) IV will be administered to the participant followed by a whole brain dynamic PET/MRI scan over 66 minutes. During the MRI sequences, the patient will receive an additional IV bolus of Gadolinium contrast medium administered through a peripheral venous cannula. Arterial blood sampling through a peripheral arterial line will be performed to determine the concentration of radiotracer within arterial plasma. All the patients that are enrolled into the study will undergo biopsy or surgical resection as part of their routine clinical care, from which their tumour grade will be confirmed; we will obtain tissue from these procedures to perform metabolomics, genomics and proteomics. Surgery or biopsy will be performed typically within 2 weeks but no later than 3 months'. In anticipation of any transformation whilst patients are awaiting surgery, we will record the exact time between imaging and surgery for each patient.

7.2 STUDY SCHEDULE

[figure not shown]
Figure 1.

7.3 Patient Identification and recruitment

Potentially eligible patients will be identified by their clinician at Charing Cross Hospital. An explanation of the study will be given by the treating clinician and they will be provided with the Patient Information Sheet (PIS) to take away. Patients will have a minimum of 24 hours to consider their participation in the trial before any trial related activities take place. After 24 hours and following verbal consent from the patient, the potential participant will be contacted by a member of the study team to answer any questions they may have regarding the study. Should they wish to participate, they will then be invited to attend a screening visit up to 21 days before tracer administration and imaging.

Figure 2. Recruitment pathway

8. ELIGIBILITY

8.1 Inclusion Criteria:

Patients with radiological evidence of suspected cerebral glioma due for surgery or biopsy and with the following characteristics will be recruited:

1. Age ≥ 18
2. Tumour size at least 2 cm.
3. WHO performance status 0 – 2.
4. If female, the subject is either post-menopausal (at least 1 year), or surgically sterilized (has had a documented bilateral oophorectomy and/or documented hysterectomy for at least 2 years), or if of childbearing potential, must have a negative urine beta human chorionic

- gonadotropin (β -HCG) pregnancy test done at initial screening and on the day of tracer administration. The result of the pregnancy test must be known before administration of ^{18}F -FPIA injection.
5. The subject is able and willing to comply with study procedures, and signed and dated informed consent is obtained.
 6. The subject has a satisfactory medical history as judged by the investigator with no significant co-morbidities, physical examination, and vital signs findings during the screening period (from 21 days before administration).
 7. The subject's clinical and laboratory tests are within normal limits and/or considered clinically insignificant.

8.2 Exclusion Criteria:

1. The subject has received any chemotherapy, immunotherapy, biologic therapy or investigational therapy within 14 days or five half-lives of a drug (whichever is longer) prior to the first dose of ^{18}F -FPIA injection. The subject is pregnant or lactating.
2. The subject is diabetic or has uncontrolled blood glucose or blood lipid levels (clinical decision by investigator), any other chronic illness that will preclude brief discontinuation of medication, or musculoskeletal condition that would not allow comfortable performance of a 66-minute scan.
3. The subject has received, or is scheduled to receive, another IMP/radioactive tracer 1 month before administration of ^{18}F -FPIA injection.
4. Anticoagulation therapy, prolonged prothrombin time, abnormal Allen's test.
5. Unsatisfactory renal function (eGFR<60)
6. The subject has non-MRI compatible devices (a pacemaker, an implantable cardioverter-defibrillator (ICD), a nerve stimulator, a cochlea implant and a drug pump) or implanted material (e.g. non-MRI compatible sternal wires, biostimulators, metals or alloys).

9. COMPLETION, WITHDRAWAL AND TERMINATION CRITERIA

9.1 Subject completion

A completed subject is one who has completed all imaging sequences of the combined ^{18}F -FPIA PET/MRI protocol.

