5. The subject is able and willing to comply with study procedures, and signed and dated informed consent is obtained.
6. The subject has a satisfactory medical history as judged by the investigator with no significant co-morbidities, physical examination, and vital signs findings during the screening period (from 21 days before administration).
7. The subject's clinical and laboratory tests are within normal limits and/or considered clinically insignificant.

Exclusion Criteria:

8. The subject has received any chemotherapy, immunotherapy, biologic therapy or investigational therapy within 14 days or five half-lives of a drug (whichever is longer) prior to the first dose of ¹⁸F-FPIA injection. The subject is pregnant or lactating.
9. The subject is diabetic or has uncontrolled blood glucose or blood lipid levels (clinical decision by investigator), any other chronic illness that will preclude brief discontinuation of medication, or musculoskeletal condition that would not allow comfortable performance of a 66-minute study.
10. The subject has received another investigational radioactive tracer within 1 month before administration of ¹⁸F-FPIA injection.
11. Anticoagulation therapy, prolonged prothrombin time, abnormal Allen's test.
12. Unsatisfactory renal function (eGFR<60)

Number of Patients Planned: 10

- In the event of unevaluable data, additional patients will be recruited to reach a total number of 10 complete patients.

Treatment of Subjects: Experimental imaging biomarker tracer:

- Subjects will receive a single I.V. bolus injection of ¹⁸F-FPIA over a period of about 30 seconds. The tracer injection will be followed by a saline flush. Patients will receive a maximum ¹⁸F activity of 370 MBq.

Statistical Methods and Planned Analysis:

- The study is an Observational Non-randomised Phase 2 study to determine the magnitude of the early steps of fatty acid oxidation in glioma using ¹⁸F-FPIA PET/MRI. This is the first time we are using FPIA in patients (with glioma), thus we do not know *a priori* the magnitude of uptake. Statistical tests will use a 0.05 significance level and will be 2-sided unless otherwise noted. 10 evaluable patients will be recruited for the study with the Upper Confidence Interval of sensitivity to detect fatty acid metabolism set to $\geq 90\%$. All patients will undergo surgical resection or biopsy for histological confirmation of tumour grade.

TABLE OF CONTENTS

- 1. SYNOPSIS**

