9.2 Rules for subject withdrawal

There are no formal withdrawal criteria for this study. During the conduct of the study, the study team will review the safety data for trends and signals that would indicate the need for withdrawal of a subject.

In accordance with the Declaration of Helsinki, each subject is free to withdraw from the study at any time. Investigator(s) also have the right to withdraw subjects from the study in the event of illness, AEs, or other reasons concerning the health or well-being of the subject, or in the case of lack of co-operation. Should a subject decide to withdraw after administration of the tracer, or should the investigator decide to withdraw the subject, all efforts will be made to complete and report the observations up to the time of withdrawal as thoroughly as possible. A complete final evaluation at the time of the subject's withdrawal will be made and an explanation given of why the subject is withdrawing or being withdrawn from the study.

The reason for non-completion and the date and time of the last contact with the subject must be noted in the research documentation. If the reason for withdrawal is a clinical AE or an abnormal laboratory result, monitoring will continue until the outcome is evident. The specific event or test result(s) must be recorded in the research documentation. In the case of subject withdrawal before or after dosing (i.e. non-evaluable subjects) additional subjects may be enrolled to reach a total of 10 evaluable subjects.

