11.4 MRI Protocol

The MRI protocol will include the following sequences:

- Sequences for attenuation correction of PET data (DIXON, zero-TE)
- Volumetric T1-weighted images, pre- and post-contrast administration
- Volumetric T2
- Dynamic susceptibility contrast perfusion (DSC)
- Dynamic contrast enhanced perfusion (DCE)

The exact image acquisition parameters for sequences (e.g. TE, TR, flip angle) are hardware dependent and vary between scanner manufacturers and models, and are therefore not specified here. DWI sequences will be acquired prior to contrast agent administration.

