11.10 MRI analysis

MRI structural imaging sequences will be used for motion correction of PET data and to define tumour volumes using semi-automated intensity based segmentation algorithms such as those available in the software 'Jim'. Perfusion data will be analysed using custom in-house image analysis tools and other software tools such as MATLAB, FSL, Nordic Neurolab and Tarquin. MRI and PET imaging

parameters will be combined to develop novel biomarkers which can be used for tumour characterisation and assessment of treatment response.

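### Does a fully imaged patient whose tumour proves not to be glioma use up one of the 10 places and distort the primary estimate?

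*Combined protocol and SAP*

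**What the plan says.** Section 8.1 admits "Patients with radiological evidence of suspected cerebral glioma due for surgery or biopsy". No criterion requires histology. Section 7.1 puts surgery or biopsy after imaging, usually within 2 weeks and at most 3 months later.

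The number 10 is described in more than one way:

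- Synopsis, Number of Patients Planned: "In the event of unevaluable data, additional patients will be recruited to reach a total number of 10 complete patients".
- Synopsis (statistical methods) and section 4.3: 10 *evaluable* patients.
- Section 7.1: "10 evaluable patients with suspected cerebral glioma on previous MRI who are due to undergo surgical resection or biopsy".
- Section 9.1: "A completed subject is one who has completed all imaging sequences of the combined" PET/MRI protocol.
- Section 9.2, on replacement: "subject withdrawal before or after dosing (i.e. non-evaluable subjects) additional subjects may be enrolled to reach a total of 10 evaluable subjects".

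The definitions list in section 2 does not contain *evaluable*. The primary endpoint in section 6.1 is "Quantitative measurement of ^{18}F -FPIA uptake in human gliomas", and the primary objective in section 5.1 likewise concerns glioma.

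**The concern.** Reading the Synopsis count of *complete* patients with section 9.1, a place is filled once the imaging is done. Section 9.2 explains non-evaluable only as withdrawn. A patient who is fully imaged, does not withdraw, and then has tissue showing something other than glioma appears to hold a place with no written trigger for replacement.

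Three things would then be at stake. The number of gliomas behind the primary estimate would depend on chance. The decision to keep or drop a non-glioma could be taken after its uptake was known. And the comparison of high-grade with lower-grade glioma, which is the study hypothesis in section 4.2, would lose the same patients. With 10 patients, each carries a tenth of the estimate.

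**Working it through.** **Step 1. Is the case really closed against replacement?** Five statements give the number. Four use *evaluable* (Synopsis statistical methods, 4.3, 7.1, 9.2) and one uses *complete* (Synopsis, Number of Patients Planned). Section 9.1 defines a completed subject and does not say that completed means evaluable. The one sentence that counts complete patients is also the one that replaces for unevaluable data, a trigger not tied to withdrawal. For an endpoint defined in gliomas, a scan of something else can fairly be called unevaluable. So the text leaves replacement open and does not rule it out.

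**Step 2. Is keep-or-drop really open?** No. Objective and endpoint are both uptake in glioma. Keeping a patient known not to have glioma would contradict them. A non-glioma also has no glioma grade, so it could not enter the grade comparison in any case. Only the number of gliomas remains uncertain.

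**Step 3. Does the plan set a target that fewer gliomas would miss?** Section 4.3 justifies 10 only by an upper confidence limit of sensitivity of at least 90%. No expected sensitivity, standard deviation (SD) or power is given, so 10 cannot be reproduced. With exact two-sided 95% limits, the condition at n = 10 is met by 7 or more positives (6/10 gives 87.8%, 7/10 gives 93.3%). At n = 9 it is met by 6 or more, and at n = 8 by 5 or more. Every n from 1 to 14 can meet it. Losing one or two patients therefore breaks no stated requirement.

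**Step 4. How often might it happen?** The documents give no rate of non-glioma histology, so q is an assumption.

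- P(at least one of 10) = 1 − (1 − q)^10
- P(at least two of 10) = 1 − (1 − q)^10 − 10q(1 − q)^9

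| Assumed q | Expected gliomas in 10 | P(at least 1) | P(at least 2) |
|---|---|---|---|
| 5% | 9.5 | 0.401 | 0.086 |
| 10% | 9.0 | 0.651 | 0.264 |
| 20% | 8.0 | 0.893 | 0.624 |

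**Step 5. What does dropping without replacement cost?** The 95% half-width for mean uptake, in SD units, is t(0.975, n − 1)/√n.

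| Gliomas | Half-width (SD) | Change from n = 10 |
|---|---|---|
| 10 | 0.715 | – |
| 9 | 0.769 | +7.5% |
| 8 | 0.836 | +16.9% |

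This yardstick is mine; the plan sets no precision goal for mean uptake.

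**Step 6. What would wrongly keeping one cost?** If its uptake lies d SD from the glioma mean, the mean of 10 moves by d/10: 0.10 SD for d = 1 and 0.20 SD for d = 2. By Step 2 this would be a departure from the plan, not a result of following it.

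**Step 7. What would compulsory replacement cost?** Expected scans for 10 gliomas are 10/(1 − q) = 10.5, 11.1 and 12.5 at q = 5%, 10% and 20%. For a 90% chance of reaching 10 gliomas, 12, 13 and 15 patients must be scanned. Each extra patient receives up to 370 × 0.0187 = 6.9 mSv (section 11.5) and an arterial cannula (section 11.2). Recruitment might stay open for up to 3 months after the last scan, waiting for histology.

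**The case for a change.** The strongest case for a change is that the text never says what happens to this patient and that a definition costs only a sentence. Histology is collected anyway. *Evaluable* has only the negative gloss in section 9.2, and that sits awkwardly with 9.1: someone who finishes imaging and then withdraws before surgery is completed under one section and non-evaluable under the other. Replacement is firm in the Synopsis and optional in 9.2. In a study of 10, a choice made after uptake is known is undesirable. At an assumed rate of 20%, two or more non-gliomas are more likely than not.

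Much of this stands as a description of loose drafting. No readable section gives a rule for non-glioma histology, although the outline and schedule figures are not legible in the available text. What does not stand is the consequence. The endpoint fixes who belongs in the primary estimate before any uptake is seen. The remaining discretion is whether to recruit a further patient, and that affects how many gliomas there are, not which scanned gliomas are analysed. Writing in a confirmed-glioma analysis set would record what the endpoint already implies. Making replacement compulsory would add research scans for a modest gain in precision.

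A side issue is that 9.1, read literally, makes a glioma patient with good PET but a failed perfusion run incomplete. Nothing in the plan requires that patient to be replaced or the PET data to be discarded. Perfusion serves a tertiary endpoint, so wanting all sequences is a defensible choice.

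**Conclusion.** No change is needed. The counting terms are inconsistent and *evaluable* lacks a positive definition, but this is a gap that analysts fill sensibly from the objective and endpoint: estimate uptake in histologically confirmed gliomas and report how many there were. The likely effect is one patient fewer, a confidence interval about 7% wider; two fewer would make it about 17% wider. Neither misses a target, because the plan states none for mean uptake and its sensitivity condition can still be met at 9 or 8. For a study the Synopsis labels explorative, whether to scan a replacement is a fair trade-off between precision and burden.

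This rests on two things: that the analyst respects the restriction to glioma, and that non-glioma findings are uncommon. The rates of 5% to 20% are assumptions. A higher rate would leave fewer gliomas and a wider interval, but would not bias an estimate confined to confirmed gliomas.

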9.2 Rules for subject withdrawal

There are no formal withdrawal criteria for this study. During the conduct of the study, the study team will review the safety data for trends and signals that would indicate the need for withdrawal of a subject.

In accordance with the Declaration of Helsinki, each subject is free to withdraw from the study at any time. Investigator(s) also have the right to withdraw subjects from the study in the event of illness, AEs, or other reasons concerning the health or well-being of the subject, or in the case of lack of co-operation. Should a subject decide to withdraw after administration of the tracer, or should the investigator decide to withdraw the subject, all efforts will be made to complete and report the observations up to the time of withdrawal as thoroughly as possible. A complete final evaluation at the time of the subject's withdrawal will be made and an explanation given of why the subject is withdrawing or being withdrawn from the study.

The reason for non-completion and the date and time of the last contact with the subject must be noted in the research documentation. If the reason for withdrawal is a clinical AE or an abnormal laboratory result, monitoring will continue until the outcome is evident. The specific event or test result(s) must be recorded in the research documentation. In the case of subject withdrawal before or after dosing (i.e. non-evaluable subjects) additional subjects may be enrolled to reach a total of 10 evaluable subjects.

9.3 Rules for terminating study

The sponsor reserves the right to terminate the study at any time. Prior to dosing of the first subject, the study may be terminated by the sponsor and the investigator without consultation with the Administration of Radioactive Substances Advisory Committee (ARSAC) holder and Ethics Committee. The ARSAC holder, Ethics Committee and Health Research Authority (HRA), must be promptly notified that the study will no longer be taking place and provided with a detailed written explanation. Once dosing with radiopharmaceutical has begun, the study may only be terminated if a careful review of the overall risk benefit analysis demonstrates that the assumptions have changed and that the overall balance is no longer acceptable. The investigators will temporarily halt the study if there has been a SAE which has been judged to be related to the study dosing. In these circumstances termination can only take place with the agreement of the Sponsor, ARSAC holder and the Ethics Committee.

If it becomes necessary to consider termination of the study after dosing has begun, dosing may be suspended pending discussion between the sponsor, the investigator, the ARSAC holder and the Ethics Committee. Dosing may always be immediately suspended for safety reasons.

10. STUDY PROCEDURES

The patient procedures are summarized in Table 1 below.

Table 1. Study Schedule of Events:

	Screening	Pre-PET/MRI dose(same day)	Dose	+ 1 min	+ 1 min	+ 1 min	+ 1 min	+ 1 min
Informed Consent	•							
Entry Criteria	•							
Demographic Information	•							
Medical History	•							
Prior/Concomitant Medication ¹	•	•						
Physical Exam including Allen's Test ¹	•	•						
Blood test for haemoglobin, clotting profile and renal function ²	•							
Carnitine blood test		•						
Pregnancy Test ¹	•	•						
Vital Signs ¹	•	•						
¹⁸ F-FPIA injection			•					
Gadolinium contrast injection 0.2ml/kg				•	•			
Simultaneous PET/MRI Imaging*				continuous				
Arterial Blood Activity Counting				•	•	•	•	•
Adverse events				•	•	•	•	•
Telephone follow up 24 hours post tracer injection								
Post biopsy or surgery, obtain tumour tissue sections for grading, gene expression, metabolomics, and proteomics								

- ¹If screening and PET/MRI are on same day – procedures do not have to be repeated.
- ²If result available from routine test within 30 days of ¹⁸F-FPIA injection, this does not need to be repeated (determined by investigator)
- Note: sampling times may be changed if necessary for scientific or logistical reasons but will not exceed the volume stated.
- *For further details regarding the MRI protocol see Section 11.4

11. IMAGING PROTOCOL

11.1 Radiopharmaceutical

The ^{18}F -FPIA radiotracer will be made to GMP standards at Imanova Limited, which is GMP certified.

